5.1.3 Subject Exclusion Criteria

The subject must be excluded from participating in the trial if the subject:

1. Has disease that is suitable for local treatment administered with curative intent.
2. Part 1: has received prior therapy with cancer vaccines, or compounds targeting PD-1 (including pembrolizumab), PD-L1, PD-L2, CTLA-4, or MEK.

Note: Examples of MEK inhibitors include, but are not limited to, trametinib and cobimetinib.

3. Part 2: has received prior therapy with cancer vaccines, or compounds targeting PD-1 (including pembrolizumab), PD-L1, PD-L2, CTLA-4, LAG-3, CD-137, OX-40, CD-40, GITR, BRAF, MEK or other molecules in the MAPK pathway.

Note: Examples of BRAF inhibitors include, but are not limited to, dabrafenib and vemurafenib.

4. Is currently participating in or has participated in a study of an investigational agent or using an investigational device within 4 weeks prior to the first dose of trial treatment.
5. Has taken during the 14 days prior to enrollment, or is currently taking medication that interferes with CYP3A4 or CYP2C8 as listed in [Table 8](#).
6. Has Gilbert's Syndrome.
7. Has a diagnosis of immunodeficiency or is receiving chronic systemic steroid therapy (in doses exceeding 10 mg daily of prednisone equivalent) or any other form of immunosuppressive therapy within 7 days prior to the first dose of trial treatment. The use of physiologic doses of corticosteroids may be approved after consultation with the Sponsor.
8. Has had a prior anticancer mAb within 4 weeks prior to study Day 1 or who has not recovered (ie, \leq Grade 1 or at baseline) from AEs due to agents administered more than 4 weeks earlier.
9. Has had prior chemotherapy, targeted small molecule therapy, or radiation therapy within 14 days prior to study Day 1 or who has not recovered (ie, \leq Grade 1 or at baseline) from AEs due to a previously administered agent.

Note: Subjects with \leq Grade 2 neuropathy or \leq Grade 2 alopecia are an exception to this criterion and may qualify for the study upon consultation with the Sponsor.

Note: If subject received major surgery, they must have recovered adequately from the toxicity and/or complications from the intervention prior to starting therapy.

10. Has received transfusion of blood products (including platelets or red blood cells) or administration of colony stimulating factors (including granulocyte-colony stimulating factor [G-CSF], granulocyte-macrophage colony-stimulating factor [GM-CSF] or recombinant erythropoietin) within 4 weeks prior to study Day 1.
11. Has a known additional malignancy that is progressing or requires active treatment. Exceptions include basal cell carcinoma of the skin, squamous cell carcinoma of the skin that has undergone potentially curative therapy, or in situ cervical cancer.
12. Has known active central nervous system metastases and/or carcinomatous meningitis.

Note: Subjects with previously treated brain metastases may participate provided they are stable (without evidence of progression by imaging, using the identical imaging modality for each assessment, either MRI or CT scan) for at least 4 weeks prior to the first dose of trial treatment and any neurologic symptoms have returned to

baseline, have no evidence of new or enlarging brain metastases, and are not using steroids for at least 14 days prior to trial treatment. This exception does not include carcinomatous meningitis which is excluded regardless of clinical stability.

13. Active autoimmune disease that has required systemic treatment in past 2 years (ie, with use of disease modifying agents, corticosteroids, or immunosuppressive drugs). Replacement therapy (eg, thyroxine, insulin, or physiologic corticosteroid replacement therapy for adrenal or pituitary insufficiency) is not considered a form of systemic treatment and is allowed.
14. Has a history of (noninfectious) pneumonitis that required steroids or current pneumonitis.
15. Has a history of interstitial lung disease.
16. Has an active infection requiring systemic therapy.
17. Has a history or current evidence of any condition, therapy, or laboratory abnormality that might confound the results of the trial, interfere with the subject's participation for the full duration of the trial, or is not in the best interest of the subject to participate, in the opinion of the treating investigator.
18. Has a known psychiatric or substance abuse disorder that would interfere with the subject's ability to cooperate with the requirements of the trial.
19. Is pregnant or breastfeeding, or expecting to conceive or father children within the projected duration of the trial, starting with the screening visit through 120 days after the last dose of trial treatment.
20. Has a known history of human immunodeficiency virus (HIV) (HIV 1/2 antibodies).
21. Has known active hepatitis B (eg, hepatitis B surface antigen reactive) or hepatitis C (eg, hepatitis C virus RNA [qualitative] is detected).
22. Has received a live-virus vaccination within 30 days of planned treatment start. Seasonal flu vaccines that do not contain live virus are permitted.
23. Is expected to require any other form of systemic or localized antineoplastic therapy while in study.
24. Has severe hypersensitivity (\geq Grade 3) to pembrolizumab and/or any of its excipients.
25. Has had an allogeneic tissue/solid organ transplant.
26. Part 2: Have a histologically confirmed adenocarcinoma originating from the colon or rectum that is microsatellite instable (ie, MSI-H).

Part 2: MK-8353 will be administered at the RP2D(s) identified for MK-8353 in Part 1 of the study (several doses and schedules could be explored), in combination with pembrolizumab at a fixed dose of 200 mg (same fixed dose as in Part 1). The decision to bring specific schedule(s) or dose(s) into the expansion cohorts in Part 2 will be based on exposure parameters, as well as the safety profile and potential preliminary efficacy observed, and will be made jointly by the investigators and the Sponsor.

Throughout the study (Part 1 and Part 2) in Arms A and B, the first dose of MK-8353 will occur at the trial site on Day 1 of each cycle, shortly before the pembrolizumab infusion. Pembrolizumab will be then administered through an IV infusion as described in the Pharmacy Manual. For optional Arm C, administration will follow the schedule described in **Table 2**. For optional Arm D, after the screening visit, the subject will receive MK-8353 monotherapy unsupervised at his/her home from Cycle 1, Day 1 to Day 14, prior to Cycle 2 Day 1.

1. Arm A (bid continuous):
 - For the cohorts in Arm A (bid schedule), subsequent dosing of MK-8353 will be performed in the evening of the same day (Day 1), and then twice a day by the subject (ie, unsupervised at his/her home) at approximately the same time each day, until Day 1 of the next cycle.
2. Arm B (qd continuous):
 - In Arm B (qd schedule), subsequent dosing of MK-8353 will be performed the next day (Day 2), and then once a day by the subject (ie, unsupervised at his/her home) at approximately the same time each day, until Day 1 of the next cycle.

3. Optional Arm C (1 week on/1 week off):

- In optional Arm C (1 week on/1 week off qd schedule), subsequent dosing of MK-8353 will be performed the next day by the subject (ie, unsupervised at his/her home) at approximately the same time each day, on Days 1 to 7, Days 15 to 21, and Days 29 to 35 of a 42-day period (corresponding to 2 cycles of 21 days) until Day 1 of Cycle 3.

4. Optional Arm D (monotherapy run-in then continuous):

- In optional Arm D (monotherapy run-in then qd continuous), MK-8353 will be administered qd from Cycle 1, Day 1 to Day 14 (ie, unsupervised at his/her home), prior to Cycle 2 Day 1. Cycle 2 Day 1 will be performed at the clinical site. Subsequent dosing of MK-8353 will be performed the next day (Cycle 2 Day 2), and then once a day by the subject (ie, unsupervised at his/her home) at approximately the same time each day, until Day 1 of the next cycle.

Enrollment will be accomplished by nonrandom assignment to each combination treatment dose level in Part 1, using an interactive voice response system/integrated web response system (IVRS/IWRS). In Part 2, if several schedules and/or doses at RP2D are explored for the combination therapy, assignment will be randomized. Enrollment will be semi-competitive between sites.

All supplies indicated in [Table 2](#) above will be provided centrally by the Sponsor or locally by the trial site, subsidiary or designee, depending on local country operational or regulatory requirements.

The investigator shall take responsibility for and shall take all steps to maintain appropriate records and ensure appropriate supply, storage, handling, distribution and usage of trial treatments in accordance with the protocol and any applicable laws and regulations.

5.2.1 Dose Selection

5.2.1.1 Dose Selection (Preparation)

The rationale for selection of doses to be used in this trial is provided in Section 4.0 Background & Rationale. There are no specific calculations or evaluations required to be performed in order to administer the proper dose to each subject.

5.2.1.2 Dose Escalation and Confirmation

In Part 1 of the study, an mTPI design [1] with a target DLT rate of approximately 30% will be applied for dose escalation and confirmation to determine a RP2D for MK-8353 in combination with pembrolizumab.

In Arms A (bid continuous) and B (qd continuous), predetermined dose levels of MK-8353 (in combination with a fixed dose of pembrolizumab) will be explored independently. In Arm A, a de-escalation dose of 50 mg is available if the starting dose of 100 mg is deemed not tolerable. All dose escalation and de-escalation decisions will be based on the occurrence of DLTs at a given dose during the DLT evaluation period and will be made jointly by the

investigators and the Sponsor. In Arm B, additional intermediate dose levels between 600 and 1200 mgs may be explored.

Additionally, the investigators and the Sponsor can decide jointly to open the 2 optional schedules (Arm C and/or Arm D) based on safety information and PK data obtained from Arms A and B. All dose escalation and de-escalation decisions in these 2 arms will be also based on the occurrence of DLTs at a given dose during the DLT evaluation period (Cycle 1 for Arm C [21 days], and Cycles 1 and 2 for Arm D [35 days]) and will be made jointly by the investigators and the Sponsor.

Additional doses of 10 mg and 30 mg could be explored in any of the 4 arms based on safety information and exposure data obtained at the higher doses. The decision to explore these lower doses will be made jointly by the investigators and the Sponsor.

The dose of pembrolizumab will remain constant at 200 mg q3w for each dose level of MK-8353 and in each arm.

In [Table 3](#), the number of subjects treated is indicated in the columns and the number of subjects who experienced a DLT is indicated in the rows. Dosing decisions include escalate to the next higher dose (E), stay at the current dose (S), de-escalate to the next lower dose (D), and de-escalate to a lower dose and never test this dose again (ie, unacceptably toxic dose; DU).

During dose escalation, a minimum of 3 subjects is required at each dose. At the starting dose in Arm A (DL1A), 1 subject will be enrolled, and subsequent subjects will be enrolled once the first subject has reached Cycle 1 Day 15. Additionally, previously enrolled subjects, continuing on the study, will be able to restart MK-8353 at 100 mg bid in combination with pembrolizumab once the first subject has reached Cycle 1 Day 15. In subsequent doses for each arm, staggering enrollment is optional.

Depending on accrual rate, 3, 4, 5, or 6 subjects may be enrolled at each new dose until the last of those subjects completes the DLT assessment period. For example, the dose escalation rules will proceed as follows if 3 subjects are enrolled: if 0 out of the first 3 subjects at a given dose level develops a DLT, then the dose can be escalated to the next level without further expansion. If 1 out of the first 3 subjects at a given dose level develops a DLT, no more than an additional 3 subjects should be enrolled at this dose level until additional DLT data are available since this dose would be considered unacceptably toxic if all 3 of the additional subjects experience a DLT (ie, 4 out of 6 subjects). If 2 out of the first 3 subjects at a given dose level develop a DLT, the dose will be de-escalated to the next lower level. If 3 out of the first 3 subjects at a given dose level develop a DLT, this dose will be considered unacceptably toxic (ie, the dose will be de-escalated and never re-escalated to that dose again). The same principle will be applied whether 3, 4, 5, or 6 subjects are enrolled in the same dose cohort according to [Table 3](#).

Based on the mTPI design, the number of subjects who are enrolled at a dose, but are not yet fully evaluable for DLT assessment, may not exceed the number of remaining subjects who are at risk of developing a DLT before the dose would be considered unacceptably toxic (denoted as DU in [Table 3](#)). To determine how many more subjects can be enrolled at a dose level, one can count steps in a diagonal direction (down and to the right) from the current cell to the first cell marked DU. In total, 3 to 14 subjects may be enrolled at a given dose level.

For example, if 1/3 subjects have experienced a DLT at a given dose level, no more than an additional 3 subjects should be enrolled at this dose level until additional DLT data are available. This is because this dose level would be considered unacceptably toxic if all 3 of the additional subjects experience a DLT (ie, 4/6 subjects with DLTs as in [Table 3](#)).

This is a Phase 1b assessment of MK-8353 in humans, and the PK, PD, and safety profiles of the compound are still being elucidated. This protocol is written with some flexibility to accommodate the inherent dynamic nature of Phase 1 clinical studies. Modifications to the dose, dosing regimen and/or clinical or laboratory procedures currently outlined above may be required to achieve the scientific goals of the study objectives and/or to ensure appropriate safety monitoring of the study participants. As such, some alterations from the currently outlined dose and/or dosing regimen may be permitted based on newly available data, but the maximum daily dose may not exceed those currently outlined in the protocol, including repeat of or decrease in the dose of the study intervention administered in any given arm.

Dose escalation and confirmation will end after 14 subjects have been treated at any one of the selected doses. The pool-adjacent-violators-algorithm [1] will be used to estimate the DLT rates across doses. The dose with an estimated DLT rate closest to 30% may be treated as a preliminary MTD. The totality of the data will be considered before a dose is selected to carry forward to Part 2 and the escalation schedule may be adjusted based on PK and safety data emerging throughout the study to determine the RP2D.

Note that although 30% was the target toxicity rate used to generate the guidelines in [Table 3](#), the observed rates of subjects with DLTs at the MTD may be slightly above or below 30%.

Table 3 Dose Escalation and Confirmation Rules Based on the Modified Toxicity Probability Interval Design

Number of toxicities	Number of subjects treated at current dose											
	3	4	5	6	7	8	9	10	11	12	13	14
0	E	E	E	E	E	E	E	E	E	E	E	E
1	S	S	S	E	E	E	E	E	E	E	E	E
2	D	S	S	S	S	S	S	S	E	E	E	E
3	DU	DU	D	S	S	S	S	S	S	S	S	S
4		DU	DU	DU	D	D	S	S	S	S	S	S
5			DU	DU	DU	DU	DU	D	S	S	S	S
6				DU	DU	DU	DU	DU	DU	D	S	S
7					DU	D						
8						DU						
9							DU	DU	DU	DU	DU	DU
10								DU	DU	DU	DU	DU
11									DU	DU	DU	DU
12										DU	DU	DU
13											DU	DU
14												DU

Target toxicity rate = 30%
 Flat non-informative prior Beta (1,1) is used as a prior and $\varepsilon_1=\varepsilon_2=0.05$ [1].
 D=de-escalate to the next lower dose; DU=the current dose is unacceptably toxic, E=escalate to the next higher dose, S=stay at the current dose.

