1 TRIAL SUMMARY

Abbreviated Title	Phase 1b Study of MK-8353 + Pembrolizumab in Subjects with Advanced Malignancies
Sponsor Product Identifiers	MK-8353 and pembrolizumab
Trial Phase	Phase 1b
Clinical Indication	Treatment of Advanced Solid Tumors with a Focus on non-MSI-H/dMMR Colorectal Cancer \geq Second Line
Trial Type	Interventional
Type of control	No treatment control
Route of administration	Oral (MK-8353) and intravenous (Pembrolizumab)
Trial Blinding	Unblinded Open-label
Treatment Groups	
Part 1: Dose escalation and confirmation (modified toxicity probability interval design)
 
Arm A (MK-8353: twice daily [bid] continuous):
 
Dose level (DL)1: MK-8353 350 mg bid + Pembrolizumab 200 mg once every 3 weeks (q3w)
 
DL1A: MK-8353 50 mg bid + Pembrolizumab 200 mg q3w
 
DL2A: MK-8353 50 mg + 100 mg + Pembrolizumab 200 mg q3w (total daily dose of 150 mg MK-8353)
 
DL3A: MK-8353 100 mg bid + Pembrolizumab 200 mg q3w
 
DL4A: MK-8353 150 mg bid + Pembrolizumab 200 mg q3w
 
DL5A: MK-8353 200 mg bid + Pembrolizumab 200 mg q3w
 
DL6A: MK-8353 300 mg bid + Pembrolizumab 200 mg q3w
 
Arm B (MK-8353: once daily [qd] continuous):
 
DL1B: MK-8353 50 mg qd + Pembrolizumab 200 mg q3w
 
DL2B: MK-8353 100 mg qd + Pembrolizumab 200 mg q3w
 
DL3B: MK-8353 150 mg qd + Pembrolizumab 200 mg q3w
 
DL4B: MK-8353 200 mg qd + Pembrolizumab 200 mg q3w
 
DL5B: MK-8353 300 mg qd + Pembrolizumab 200 mg q3w
 
DL6B: MK-8353 400 mg qd + Pembrolizumab 200 mg q3w
 
DL7B: MK-8353 600 mg qd + Pembrolizumab 200 mg q3w
 
DL8B: MK-8353 900 mg qd + Pembrolizumab 200 mg q3w
 
DL9B: MK-8353 1200 mg qd + Pembrolizumab 200 mg q3w
 
Optional Arm C (MK-8353: qd 1 week on/1 week off)
 
DL1C: MK-8353 50 mg qd + Pembrolizumab 200 mg q3w
 
DL2C: MK-8353 100 mg qd + Pembrolizumab 200 mg q3w
 
DL3C: MK-8353 150 mg qd + Pembrolizumab 200 mg q3w
 
DL4C: MK-8353 200 mg qd + Pembrolizumab 200 mg q3w
 
DL5C: MK-8353 300 mg qd + Pembrolizumab 200 mg q3w
 
DL6C: MK-8353 400 mg qd + Pembrolizumab 200 mg q3w
 
DL7C: MK-8353 600 mg qd + Pembrolizumab 200 mg q3w

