2 TRIAL DESIGN

2.1 Trial Design

This is a multicenter, worldwide, open-label, nonrandomized, Phase 1b study of MK-8353 in combination with pembrolizumab in subjects with advanced solid tumors with a focus on subjects with \geq second line advanced non-MSI-H/dMMR colorectal cancer (CRC).

This study will evaluate the safety, tolerability, and preliminary efficacy of MK-8353 when administered in combination with pembrolizumab. There are 2 parts in this study, dose escalation and confirmation (Part 1) and cohort expansion (Part 2).

For each subject, RAS/RAF mutations and proficient versus deficient mismatch repair (pMMR vs. dMMR) status will be required for enrolling in the study. Archived tumor samples or newly obtained biopsies will be obtained during the screening period for assessment of these mutations and for biomarker evaluation.

In Part 1, the modified toxicity probability interval (mTPI) design [1] will be used to identify and confirm the recommended Phase 2 dose(s) (RP2D[s]) of MK-8353 in combination with a fixed dose of pembrolizumab in subjects with advanced malignancies. Subjects will be enrolled in 1 of 2 arms to receive MK-8353 in combination with pembrolizumab at a fixed dose of 200 mg, during 21-day cycles for approximately 24 months of treatment. In Arm A and Arm B, MK-8353 will be administered continuously at a starting dose of 50 mg twice daily (bid), or 50 mg once daily (qd), respectively (refer to Section 4.2.2). Enrollment will alternate between arms.

Initially, the protocol started at a dose of 350 mg bid of MK-8353 in combination with pembrolizumab and several dose levels for escalation from this initial dose were planned; however, 3 of the 4 subjects who received MK-8353 at 350 mg bid developed a Grade 3 rash and MK-8353 was discontinued at this dose for these 4 subjects (refer to Section 4.1.3.1).

The protocol was then amended (Amendment 1) to restart at a lower dose (100 mg bid) of MK-8353 in combination with pembrolizumab (Arm A) with a potential de-escalation dose of 50 mg bid; several dose levels for escalation were planned. The subject enrolled at 100 mg bid of MK-8353 in combination with pembrolizumab developed several Grade 3 toxicities, including Grade 3 rash, and the next subjects were enrolled at 50 mg bid of MK-8353 in combination with pembrolizumab (refer to Section 4.1.3.1.).

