DL3D	150	150 for Cycle 1, Day 1 to Day 14 (run-in), and Day 1 to Day 21 of subsequent cycles	200
DL4D	200	200 for Cycle 1, Day 1 to Day 14 (run-in), and Day 1 to Day 21 of subsequent cycles	200
DL5D	300	300 for Cycle 1, Day 1 to Day 14 (run-in), and Day 1 to Day 21 of subsequent cycles	200
DL6D	400	400 for Cycle 1, Day 1 to Day 14 (run-in), and Day 1 to Day 21 of subsequent cycles	200
DL7D	600	600 for Cycle 1, Day 1 to Day 14 (run-in), and Day 1 to Day 21 of subsequent cycles	200

* If 50 mg doses are not tolerable, doses of 10 mg and 30 mg may be explored.
** DL2A (150 mg daily) will be administered as a morning dose of 50 mg and an evening dose of 100 mg of MK-8353.
bid=twice daily; DL=dose level, IV=intravenous, q3w=once every 3 weeks; qd=once daily.

Each individual subject will be assigned to a single dose level of study drug. Intrasubject dose escalation is not allowed. Individual subject dose interruptions and/or dose decreases may be implemented based on toxicity as described in Section 5.2.2; however, dose adjustments should not be made during the DLT evaluation period without discussion with the Sponsor.

The decision to enroll subjects in the next dose level will be made by the Sponsor in consultation with the participating investigators after reviewing the safety and any available PK data of the previous dose level(s).

Subjects may continue on treatment until disease progression, unacceptable toxicity, investigator's decision to withdraw the subject, withdrawal of consent, development of an intercurrent condition precluding further administration of study treatment, pregnancy of the subject, failure to comply with dosing evaluations or other study requirements, or administrative reasons.

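### Section 5.2.1.2 starts Arm A at 50 mg bid but still lets earlier subjects restart at 100 mg bid, two dose levels higher, once one subject reaches Day 15; the sentence conflicts with the escalation sequence and must be reconciled

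*Combined protocol and SAP*

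**What the plan says.** Section 5.2.1.2 gives the opening rule for Arm A: "At the starting dose in Arm A (DL1A), 1 subject will be enrolled, and subsequent subjects will be enrolled once the first subject" reaches Day 15 of Cycle 1. The next sentence adds that "previously enrolled subjects, continuing on the study, will be able to restart MK-8353 at 100 mg bid in combination with pembrolizumab", on that same Day 15 condition.

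The Trial Summary defines the two levels as "DL1A: MK-8353 50 mg bid + Pembrolizumab 200 mg q3w" and "DL3A: MK-8353 100 mg bid + Pembrolizumab 200 mg q3w". DL2A, at 150 mg per day, lies between them. Table 2 and Table 4 agree. Sections 2.1, 4.2.2.1 and 5.2.1.4 all give 50 mg bid as the current Arm A start.

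Section 5.2.1.2 also states: "During dose escalation, a minimum of 3 subjects is required at each dose". Section 5.2.1.5 sets the Arm A DLT window at Cycle 1, 21 days.

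On experience at the restart dose, Section 2.1 says: "The subject enrolled at 100 mg bid of MK-8353 in combination with pembrolizumab developed several Grade 3 toxicities, including Grade 3 rash". It adds that the next subjects went to 50 mg bid. It also reports Grade 3 rash in 3 of the 4 subjects treated at 350 mg bid, with MK-8353 discontinued at that dose for all four.

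An earlier paragraph of Section 5.2.1.2 still describes 100 mg as the Arm A starting dose and 50 mg as the de-escalation dose.

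**The concern.** The restart sentence opens a dose that the escalation has not reached. On the current ladder, a new subject can receive 100 mg bid only after DL1A and then DL2A have each been cleared under Table 3. An earlier subject can receive it after a single DL1A subject reaches Day 15. As worded, that subject does not even have to be free of DLT; reaching Day 15 is enough.

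At stake is the safety logic of Part 1. The subjects who could use the permission come from cohorts in which severe toxicity had been reported, and the one documented experience at the restart dose was poor. A site following this paragraph literally would be acting against the escalation sequence set out in the same section. Correcting only the 100 mg starting-dose sentence would leave the permission in place.

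**Working it through.** **1. Size of the gap, reproducing Table 4.** Daily dose is the sum of the morning and evening doses.
- DL1A: 50 + 50 = 100 mg
- DL2A: 50 + 100 = 150 mg
- DL3A: 100 + 100 = 200 mg

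These match Table 4. The restart dose is two levels above DL1A, and 200/100 = 2.0 times its daily dose.

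**2. Release condition against the escalation rule.**
- Restart: 1 subject, at Day 15. The window has 21 − 15 = 6 days still to run.
- Escalation: at least 3 subjects at DL1A and 3 at DL2A, so 3 + 3 = 6 subjects before DL3A opens. With 3 subjects, Table 3 escalates only on 0 DLTs.

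**3. What one subject can show.** The inputs are those under Table 3: Beta(1,1) prior, target 30%, both margins 0.05. Recomputing the mTPI decisions from these inputs, with DU assigned when the posterior probability of a rate above 30% exceeds 0.95, reproduced every filled cell for 0 to 6 toxicities. The rows for 7 and 8 toxicities are broken in the extracted text and were not checked.

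After 0 DLTs in n subjects the posterior is Beta(1, 1 + n), so P(rate > 0.30) = 0.70^(n+1).
- 0 of 1: 0.70^2 = 0.49
- 0 of 3: 0.70^4 = 0.24

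At a true DLT rate of 30%, a single subject followed for the whole window shows no DLT with probability 0.70; three subjects all show none with probability 0.70^3 = 0.34. One clean subject therefore says little. The bare mTPI calculation would already return E at 0 of 1. It is the three-subject minimum that prevents this, and even then E moves one level, to DL2A. The restart sentence has no such minimum and passes over DL2A.

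**4. Where the sentence probably comes from.** Section 2.1 says Amendment 1 restarted the trial at 100 mg bid with 50 mg bid as the de-escalation dose. Under that design the sentence is coherent: one new subject begins at the starting dose, and earlier subjects rejoin at that same dose after Day 15. Amendment 3 starts Arm A at 50 mg bid. The 100 mg starting-dose sentence fits the same history. This is an inference from the text, not something the protocol states.

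**5. Who could still be affected.** Amendment 03 is dated 29-AUG-2017. Treatment is limited to 35 cycles: 35 × 21 = 735 days, about 24 months. A subject first dosed no later than that date would finish around early September 2019, barring long interruptions or retreatment. The current version, Amendment 07, is dated 28-JUN-2021.

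**The case against.** The strongest reply is that this is leftover text with almost no live consequence. It shares its origin with the 100 mg starting-dose sentence, one edit would cover both, and the dates suggest that the earlier subjects left treatment before the current version was issued. The wording is permissive, and dose decisions are taken jointly by investigators and sponsor. Most of this stands. It lowers the practical urgency but does not make the sentence correct.

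Three stronger readings are tempting, and the documents do not support them.

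- **A breach of the single-dose-level rule, or an intrasubject escalation.** Section 5.2.1.4 does say "Each individual subject will be assigned to a single dose level of study drug", but it also allows toxicity-based decreases. For subjects first given 350 mg bid (700 mg/day), 200 mg/day is 200/700 = 29% of their original dose. For the subject first given 100 mg bid it is no increase. The difficulty is that the dose exceeds the level under test, not that it exceeds what these subjects had received.
- **A count of five exposed subjects.** Adding the 4 at 350 mg bid to the 1 at 100 mg bid gives five, but Section 5.2.1.2 does not identify who is meant or how many were continuing. On the Amendment 1 reading, the 100 mg bid subject is the trigger, not a restarter. Section 4.1.3.1, cited for these subjects, is only partly available in the text examined.
- **A distorted DLT rate at DL3A.** Section 8.5.1 ties DLT evaluability to the 21 days following a subject's initial dose of the treatment assigned. Nothing moves restarted subjects into the DL3A column of Table 3. The point is unaddressed, not demonstrated.

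**Conclusion.** The inconsistency is real and rests on the current text alone. An operative sentence permits dosing two levels above, and at twice the daily dose of, the stated Arm A start. It does so on one subject at Day 15 of a 21-day window, and despite the reported Grade 3 toxicities in the only subject treated at that dose. It cannot be followed together with the mTPI sequence in the same section.

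The likely practical effect is small. The number of subjects who could use the permission is unknown and may be zero. That estimate assumes the earlier subjects were first dosed by the date of Amendment 03 and had no long interruption or retreatment. The Amendment 1 origin is likely but inferred. Which dose or restart condition is right is for the sponsor and investigators to decide.

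**What to change.** In the next amendment, reconcile the restart sentence and the 100 mg starting-dose sentence in Section 5.2.1.2 with Sections 2.1, 4.2.2.1 and 5.2, Table 4 and the mTPI sequence. The sponsor should state whether any restart of earlier subjects is still permitted and, if so, on what dose-level clearance it depends.

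As a clarification only, confirm that restarted, previously exposed subjects are not counted in Table 3 or in the DLT rate at the restart dose.

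The cost is one or two sentences, with no additional subjects and no change to the analysis.
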